## Version history

Version	Section	Changes	date
1.0	-	Initial version	05.03.2024
2.0	Entire document	Editorial adjustments	22.07.2024
	1.4 Study synopsis 3.2 Exclusion criteria	Specification of the exclusion criterion "OP small pelvis"	
	1.4 Study synopsis 6.3 Schedule 10.4 Final report and publication	Extension of the recruitment period, corresponding adjustment of the schedule	
2.1	1.4 Study synopsis 3.2 Exclusion criteria 8.3 Secondary endpoints	Two additional secondary endpoints were added, control group was described in more detail	14.11.2024
	5.3 Therapy failure	Definition of treatment failure was specified in more detail	
	8.8 Statistical analysis	Subgroup analyses were carried out in more detail specified	
	A1.2 Appendix	I-QOL: Urinary Incontinence Quality of Life Scale has been corrected and completed	

Kranus Health GmbH\_DINKS

### 1.3 Summary

Urinary incontinence in women is a very common clinical picture in which uncontrolled urine loss is the main symptom. Incontinence complaints are divided into stress incontinence, urge incontinence and mixed urinary incontinence. In Germany, around 15-25% of women are affected by various forms of urinary incontinence [1]. The frequency increases with age. A high number of unreported cases can be assumed [2]. Various treatment options are available for the different forms of incontinence, including lifestyle changes, physiotherapy and pelvic floor muscle training, micturition monitoring, as well as medication and finally surgical procedures.

Despite the recommendations of the guidelines [2, 3] and proven effectiveness [4] as a primary therapy, comprehensive, multimodal therapy and monitoring programmes (bladder diary, pelvic floor training, lifestyle changes, fluid management, bladder training) for female incontinence are rarely offered in clinical practice. The reason for this is the complexity of organisation and implementation in the "analogue" world. Although the attending physician has contact persons (e.g. physiotherapists) available for the individual modules, close and cross-module monitoring of patients, which is essential for the success of treatment [2, 5], cannot be realised in clinical practice. A digital health application (DiGA) can make it possible to implement the treatment concepts recommended in the guidelines and thus close a gap in care.

The positive care effect of such a DiGA is to be demonstrated in a randomised study for patients with stress incontinence (N39.3), urge incontinence (N39.42) and mixed forms of the two types of incontinence. In the intervention arm, patients receive access to a 12-week digital therapy programme (smartphone, tablet), which includes pelvic floor muscle training, bladder training, micturition diary and knowledge content for self-education. In the control arm, the previous treatments are continued. Patients in the control arm will then be given access to the digital therapy programme after the study is completed. The aim of the study is  
Among other things, evidence of improvement in disease symptoms, quality of life and patient autonomy.

Kranus Health GmbH\_DINKS

## 1.4 Study synopsis

Title of the study:	Prospective randomised study on multimodal self-treatment of women with incontinence complaints using a digital health application
Abbreviation of the study (acronym):	DINKS (Digital Incontinence Study )
Number of study centres:	1
EudraCT number:	2024-512094-27-00
EUDAMED-No. UDI-DI:	PP11745MICTERA96
Planned number of study participants:	198
Scientific management:	[name] [name] Clinic and Polyclinic for Urology and Paediatric Urology University Medicine Johannes Gutenberg University Mainz [name]
Diagnoses:	assigned to the female sex at birth ≥ 18 years with incontinence of different (stress incontinence, urge incontinence, mixed incontinence)  ICD-10 codes: - N39.3 Stress incontinence [stress incontinence] - N39.42 Urge incontinence
Study design/methodology:	Randomised, controlled, 2-arm study, single-blind, monocentric.  Arm A: Intervention through digital therapy in addition to real-life care (Intervention group; multimodal self-treatment of incontinence)  Arm B: No access to digital therapy, access is granted after the end of the study, patient continues to have access to normal care reality (control group; waiting group design)  Duration of the intervention: 12 weeks

Kranus Health GmbH\_DINKS


Goals of the clinical trial/objectives:
	
This superiority study is intended to demonstrate the following objectives:
 
Primary objective:
 
 
● Reduction in the frequency of incontinence episodes
 
 
(IEF) Secondary objectives:
 
 
● Improvement of disease symptoms in the ICIQ-SF
 
● Improving the quality of life in the I-QOL
 
● Improvement in the PAM-13 questionnaire (patient activation)
 
● Superiority in the PGI-I questionnaire (overall improvement after treatment)
 
● Increase in the proportion of patients without incontinence (cured patients)
 
● Reduction in micturition frequency during the day and at night
 
● Reduction of template consumption (pad use)
 
● Reduction of the imperative urge to urinate
 
● Improvement of functional bladder capacity
 
● Reduction in body weight
 
● Reduction of the share of patients with treatment failure
 
● Increase in the proportion of patients with a reduction in IEF from baseline to week 12 by at least 50%
 
● Reduction of the frequency of stress incontinence episodes in the S/U-IQ
 
● Reduction in the frequency of urge incontinence episodes in the S/U-IQ
 

--	--

Kranus Health GmbH\_DINKS


Target values/criteria/endpoints:
	
Primary endpoint:
 
(1) Relative change (rel-CfB-IEF) in IEF from baseline to week 12 relative to baseline; desired reduction in mean relative IEF by 50% [6] [7]; IEF per 24 hours - averaged over 72 hours
 
Secondary targets / secondary target criteria:
 
(2) Change (CfB) in the ICIQ-SF from baseline to week 12; expected mean difference between the groups of <math>\geq 2.9</math> points [8, 9]
 
(3) Change in I-QOL from baseline to week 12; expected mean difference between the groups of <math>\geq 6.3</math> points [9]
 
(4) Change in the PAM-13 questionnaire from baseline to week 12
 
(5) PGI-I questionnaire (overall improvement after treatment) at week 12
 
(6) Share of the patients without incontinence (cured patients) at the end of the study
 
(7) Change in micturition frequency per day from baseline to week 12
 
(8) Change in micturition frequency at night from baseline to week 12
 
(9) Change in pad consumption from baseline to week 12
 
(10) Change in imperative urge to urinate from baseline to week 12
 
(11) Change in functional bladder capacity from baseline to week 12
 
(12) Change in body weight from baseline to week 12
 
(13) Proportion of patients with treatment failure within the study period
 
(14) Proportion of patients with at least 50% reduction in IEF from baseline to week 12
 
(15) Change in stress incontinence episodes of the S/U-IQ from baseline to week 12
 
(16) Change in urge incontinence episodes of the S/U-IQ from Baseline at week 12

--	---


number of patients:
	
Randomised: Arm A to Arm B in a 1:1 ratio
 
Planning of study size (case number planning)
 
 
1. Relative reduction in incontinence episodes (rel-CfB-IEF), desired improvement of 50%, Minimum Important Difference (MID) approx. 45% from Yalcin 2010; significance level <math>\alpha = 5\%</math> 2-sided and Power <math>1 - \beta = 90\%</math>: <math>N = 2 \times 44 = 88</math>; + 30% due to drop outs and their conservative imputation as well as subgroup analyses: N= 120
 
2. ICIQ-SF: <math>d = 2.9</math> MID from Nyström et al., 2015 and Asklund et al., 2017  Significance level <math>\alpha = 5\%</math> 2-sided and power <math>1 - \beta = 90\%</math>: <math>N = 2 \times 44 = 88</math>; + 20% due to drop outs and their conservative imputation: <math>N = 110</math>
 
3. I-QOL: <math>d = 6.3</math> (MID) from Yalcin et al., 2006  Significance level <math>\alpha = 5\%</math> 2-sided and power 80%: due to drop outs and their conservative imputation: <math>N = 158 + 40 = 198</math>
 
4. PAM-13: CfB with desired improvement by 6 points vs. control (MCID = 6, i.e. approx. 15% of the PAM rank from 13 - 52 and from John, 2020) by <math>d/s = 6/12 = 0.5</math> (with <math>\alpha = 5\%</math> 2-sided and power = 80%: <math>N = 2 \times 64</math>.
 
 
Based on these calculations, a case number of 198 is planned.

Inclusion criteria:
	
 
● ICD-10 codes:  N39.3 Stress incontinence N39.42 Urge incontinence  Mixed incontinence
 
● Persons assigned to the female sex at birth with urge incontinence, stress incontinence, mixed incontinence (IE <math>\geq 1</math> per day)
 
● Age <math>\geq 18</math> years
 
● Mastery of the German language
 
● Internet access
 
● Tablet or smartphone access (Android not older than version 7 and iPhone not older than iPhone 9)
 
● Informed Consent: Written consent of the participating patients
 

Kranus Health GmbH\_DINKS


Exclusion criteria:
	
 
1. Absolute exclusion criteria that can be coded according to ICD-10 (incl. ICD-10 codes): 
 
● None
 
 
 
2. Absolute exclusion criteria that cannot be coded according to ICD-10: 
 
● None
 
 
 
3. Relative exclusion criteria that can be coded according to ICD-10 (incl. ICD-10 codes): 
 
● Acute cystitis N30.0
 
● Urinary bladder calculi N21.0
 
● Conservative not controllable, recurrent macrohaematuria R31
 
● Newly diagnosed bladder carcinoma < 3 months C67
 
 
 
4. Relative exclusion criteria that cannot be coded according to ICD-10: 
 
● Inability physically participate in the to participate in the therapy programme
 
● Active pregnancy
 
● Botulinum toxin treatment of the urinary bladder in the last 6 months
 
 
 
5. Study-specific methodological exclusion criteria: 
 
● Generally patients who are unable to understand and sign the consent form independently
 
● Newly initiated drug or physical therapy for micturition symptoms (anticholinergics, beta 3 receptor agonists, phytopharmaceuticals, biofeedback, EMS) in the last 4 weeks
 
● Severe psychiatric disorders that make it impossible to use the app
 
● Neurological diseases that affect the urinary tract
 
● Tumour and incontinence operations in the small pelvis
 
● Obesity per magna (BMI >35)
 
● Recurrent urinary tract infections N39.0 (at least 2 within 6 months or 3 infections within one year)
 
● Participation of the patient in another clinical trial within the last 4 weeks prior to the Inclusion
 
 
 

----------------------------	---

Kranus Health GmbH\_DINKS

	
 
● addiction or other illnesses that do not allow the person concerned to assess the nature, scope and possible consequences of the clinical trial
 


Treatments/procedures Treatment plan (incl. aftercare):
	
The digital therapy to be tested via app contains the following components:
 
 
● Micturition diary
 
● Pelvic floor training and physiotherapy exercises
 
● Bladder training / cognitive behavioural therapy
 
● Mental exercises             
 
○ Mindfulness
 
○ Progressive muscle relaxation (PMR)
 
○ Stimulus control methods
 
 
 
● Acute urge control
 
● Knowledge section / Nutrition section
 
● Progress tracking and motivation
 
 
The therapy instructions are available at via a smartphone. /tablet-based app in the form of audio, video and text. The medical benefit is assessed via self-reported data points and validated questionnaires from the baseline survey compared to the end of the survey after 12 weeks.

Timetable (duration of study):
	
Patient-centred:
 
Duration of study-related measures: 12 weeks
 
follow-up period: 12 months
 
Study-related:
 
Recruitment phase: 01.04.2024 to 31.10.2024
 
Start date: 01.04.2024
 
Treatment duration: 12 weeks
 
End of study: 15.02.2025
 
Final report: 15.04.2025

Test centres:
	
Clinic and Polyclinic for Urology and Paediatric Urology University Medicine Johannes Gutenberg University Mainz [name]

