### 8.4 Planning the scope of the study (case number planning)

Randomised: Arm A to Arm B in a 1:1 ratio

Planning the scope of the study for comparisons between the groups:

- IEF: Relative reduction in incontinence episodes (rel-CfB-IEF) with desired improvement of 50%, Minimum Important Difference (MID) approx. 50% from Yalcin 2010; at  $d/s = 0.7$  with significance level  $\alpha = 5\%$  2-sided and power  $1 - \beta = 90\%$ :  $N = 2 \times 44 = 88$ , + 20% due to drop outs and their conservative imputation as well as subgroup analyses:  $N = 120$ .
- ICIQ-SF: CfB with desired improvement by  $d = 2.9$  vs. control (MID = 2.5 from Nyström 2014 and Asklund 2017) by  $d/s = 2.9/3.2 = 0.9$  with  $\alpha = 5\%$  2-sided and power  $1 - \beta = 90\%$ :  $N = 2 \times 28$ .
- I-QOL: CfB with desired improvement by 6.3 vs. control (MID= 6.3 from Yalcin 2006) by  $d/s = 6.3/14 = 0.45$  (with  $\alpha = 5\%$  2-sided and power = 80%:  $N = 2 \times 90$ ).

Kranus Health GmbH\_DINKS

- PAM-13: CfB with desired improvement by 6 points vs. control (MCID= 6, i.e. approx. 15% of the PAM rank from 13 - 52 and from John, 2020) by  $d/s = 6/12 = 0.5$  (with  $\alpha = 5\%$  2-sided and power = 80%:  $N = 2 \times 64$ ).

Due to drop-outs and their conservative imputation, the total number of cases is set at 2 x 99 study participants for the evaluation of the primary endpoints.

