## Kranus Health GmbH\_DINKS

Multiplicity: The primary endpoint (1) and the first 3 secondary endpoints (2) - (4) are tested sequentially according to the method of a priori ordered hypotheses: The primary endpoint (1) relative change rel-CfB-IEF week 12 with respect to baseline of incontinence episodes is analysed using an analysis of covariance with the factor treatment group and the baseline value of the IEF as covariate; the significance level is 5% 2-sided. If significance is reached for endpoint (1), endpoint 2 (change in the ICIQ-SF questionnaire) is tested analogue to the 5% 2-sided level. If significance is reached for endpoint (2), endpoint (3) (change in quality of life in the I-QOL questionnaire) is tested 2-sided analogue to the 5% level. If significance is reached for endpoint 3, endpoint 4 (PAM-13) is tested 2-sided analogue to the 5% level. The other endpoints are analysed descriptively with p-values and 95% CIs. The FAS (ITT) is the primary evaluation collective for efficacy; missing values for the main outcome variables (1) - (4) are imputed using the JtR method.

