## Kranus Health GmbH\_DINKS

- Type of delivery,
- Time since last delivery
- Duration of illness,
- Pre-existing pelvic floor course,
- Non-bladder-specific medication,
- Frequency of use of the app.

The I-QOL and ICIQ are also analysed individually.

The results of the subgroup analyses are also graphically presented and summarised using forest plots.

Evaluation collectives:

- Full Analysis Set (FAS) contains all patients who were randomised. Patients who withdrew their consent immediately after randomisation are not included in this data set.
- Per-Protocol Set (PPS) contains all FAS patients from whom no significant study protocol violations were reported.
- Complete cases (CCS): Patients with complete data per evaluation.
- Safety Set (SAF) contains all patients who are included in the study (signed informed consent form). It is expected that SAF and FAS are identical.

Sensitivity analyses are carried out:

1. CCS analysis
2. FAS analysis with last-observation-carried-forward-option (LOCF).

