### 8.12 Data collection/documentation forms

In order to achieve the study objective, it is necessary to collect and process medical data from individual patients. Data is collected using electronic questionnaires, which are completed by the patients at the beginning (baseline) and at the end of the study (PROM).

The data to be analysed from the patients is collected in the app on the one hand and via an ePRO system on the other, and the latter is stored in an eCRF. The questionnaires, which are to be completed independently at the beginning (baseline/V1) and at the end of the study (V3), are collected via an ePRO system and stored in the EvidentIQ software. Further technical parameters are listed in the separate document "Confirmation of validation of EvidentIQ Germany's Marvin software and secure data hosting".

A detailed statistical analysis plan (SAP) is created before the evaluation.

Kranus Health GmbH\_DINKS

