### 9.3 Data protection

As part of the study, it is necessary to collect and process personal data from the study participants (e.g. full name, initials of first name and surname, date of birth, address) and data on treatment and the course of the disease (e.g. medical findings, types of treatment, prescribed medication). This data is generated by the patients themselves and stored electronically on the study server in pseudonymised form (i.e. without direct reference to the patient's name) with the help of a patient identification number, transmitted to the responsible data processing body and evaluated.

The trial participants will be informed about the disclosure of their pseudonymised data to the recipients named therein as part of the documentation and notification obligations. Persons who do not consent to the disclosure will not be included in the clinical trial.

If patients withdraw their consent to the study, including further data collection, no further data will be collected from the time of withdrawal. The data collected to date will continue to be used and analysed within the study, but can be deleted at the patient's request during the study period. If a patient only cancels the study treatment, the data required for the study can continue to be collected and used as long as the patient has not withdrawn their consent.

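### Sections 1.4 and 8.4 give different I-QOL bases (158 and 2 × 90) for the same difference and power, and the step from 158 to 198 is not shown to cover conservative imputation as well as drop-out

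*Combined protocol and SAP*

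**What the plan says.** Section 1.4 (number of patients, item 3) plans I-QOL for a difference of 6.3 points at two-sided 5%. It gives "power 80%: due to drop outs and their conservative imputation", followed by 158 + 40 = 198. It prints no SD and no drop-out percentage for this endpoint. The line above it, for ICIQ-SF, does print a rate: "20% due to drop outs and their conservative imputation", taking 88 to 110.

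Section 8.4 plans I-QOL for the same 6.3 points, two-sided 5% and 80% power. It prints the standardised effect as 6.3/14 = 0.45 and the base as 2 × 90. Its closing sentence attributes the total to losses and to "conservative imputation, the total number of cases is set at 2 x 99 study participants for the evaluation of the primary endpoints", again without a rate.

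Section 8.8 makes the full analysis set (FAS) the primary efficacy set and says that "missing values for the main outcome variables (1) - (4) are imputed using the JtR method". I-QOL is endpoint (3) in that list. JtR is jump-to-reference.

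The endpoint list in section 1.4 reads "Change in I-QOL from baseline to week 12; expected mean difference between the groups of" at least 6.3 points. It does not say whether this is the difference among patients with week-12 data or the difference in the FAS after imputation.

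**The concern.** There are two separate matters.

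First, one calculation has two bases. I-QOL is the only item in section 1.4 that reaches 198, so it determines the trial size. A reader who wants to know what attrition the trial was sized for gets a different answer from each section.

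Second, both sections say the total allows for drop-outs and for their conservative imputation. Replacing lost patients restores the number of completers. JtR does something else: it keeps the losses in the analysis and gives missing intervention patients the control-arm course, which shrinks the estimated difference. An allowance that only replaces losses does not pay for that shrinkage. I-QOL is third in the fixed testing sequence and the gate to PAM-13, so its power under the planned analysis matters for two of the four confirmatory tests.

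**Working it through.** **Inputs.** Difference 6.3 (1.4 and 8.4); SD 14, so d/s = 0.45 (8.4 only); two-sided 5%; power 80%; 1:1 allocation; 99 per arm. The share imputed, the baseline–change correlation and the JtR variance method are not in the documents and are varied below as assumptions.

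**1. Reproducing the bases.** Normal approximation: n per arm = 2 × (1.960 + 0.842)² / 0.45² = 15.70/0.2025 = 77.5, so 78. The two-sample t calculation gives 78.5, so 79 per arm and N = 158. The base in 1.4 reproduces with 8.4's SD.

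| n per arm | t-test power at d/s = 0.45 |
|---|---|
| 79 | 80.3% |
| 90 | 85.1% |
| 99 | 88.3% |

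Ninety per arm gives 80% only at d/s = 0.42, which is an SD of 6.3/0.42 = 15.0, not the printed 14.

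**2. What 198 allows.**
- From 158: 158/0.8 = 197.5, rounded to 198; 40/198 = 20.2% loss.
- From 180: 18/198 = 9.1% loss. A 20% loss would need 180/0.8 = 225.
- The ICIQ-SF line follows the same rule at its stated 20%: 88/0.8 = 110.

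So the 40 matches a 20% drop-out allowance on the 158 base. That the I-QOL rate is 20% is an inference, because it is not written.

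**3. What replacement of losses buys.** At 20% loss, 99 × 0.8 = 79.2 completers per arm give 80.4% power in a complete-case analysis. All 40 are used for that.

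**4. The planned analysis, if 6.3 is the completer difference.** With a share m of intervention patients imputed by JtR, the expected difference is 6.3 × (1 − m). At m = 20% it is 5.04, or 5.04/14 = 0.36. With 99 per arm and the standard error taken at full N, 0.36 × √(99/2) = 2.53, and power is Φ(2.53 − 1.96) ≈ 0.72 (t version 71.2%).

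| Share imputed | Power, full-N SE, no covariate gain |
|---|---|
| 5% | 84.9% |
| 10% | 80.9% |
| 15% | 76.4% |
| 20% | 71.2% |

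The 80% level is met up to about 11% imputed with this standard error, and up to 7.5% with a standard error from observed patients only.

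A simulation of the planned model used 99 per arm, data missing completely at random at 20%, 20 imputations from the control regression on baseline, ANCOVA and 3,000 replicates. The mean estimate was 5.03. The table sets its Rubin's-rules power beside the full-N figure.

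| Baseline–change correlation | Rubin's rules | Full-N SE |
|---|---|---|
| 0 | about 64% | 71% |
| 0.3 | about 68–69% | 75% |
| 0.5 | about 77% | 83% |

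With a repeated-sampling standard error and no correlation, the simulation gave 78%.

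**5. The other confirmatory endpoints at 20% imputed.** PAM-13 (d/s = 0.5, diluted to 0.40): 80.0% with a full-N standard error, with a closed-form lower bound of 70.6%. IEF (d/s = 0.7): 94% or more. ICIQ-SF (d/s = 2.9/3.2): above 99%.

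**The case against.** The certain error is small and on the safe side: 2 × 90 overstates the need, and 198 is the planned total throughout. That stands, and it is why no change to N is proposed. It is not quite harmless, because taking 180 as the base cuts the apparent loss allowance to 9%.

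The 20% is easy to recover, since 158 + 40 follows the ICIQ-SF rule one line above. That is fair for section 1.4 read alone. It does not fit the base printed in 8.4.

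The stronger reading a reader might infer is that I-QOL is underpowered, or that the trial should have been larger: 158/0.8² = 247 at 20% imputed. The documents do not support that:
- The rate is not stated for I-QOL, nor is the share of losses that would be imputed.
- Section 8.8 limits that share: "Patients who withdrew their consent immediately after randomisation are not included in this data set". If half of a 20% loss left the FAS this way, 89.1 per arm would remain with 11.1% imputed, and power would be about 71–76% (closed-form bound to full-N standard error).
- Section 9.3 limits it further: "If a patient only cancels the study treatment, the data required for the study can continue to be collected and used".
- Section 1.4 writes the I-QOL difference as a minimum, and 8.8 makes the FAS primary. Reading 6.3 as the FAS difference is therefore reasonable, and on that reading 80% is kept.
- ANCOVA with baseline is planned, so the zero-correlation figures are the unfavourable end.

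Finally, version 2.1 is dated after the scheduled end of recruitment, so restating power now serves the record and the reading of the results, not the conduct of the trial. That also stands.

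**Conclusion.** Wrong as written, with no assumption beyond the printed inputs: section 8.4's 2 × 90 does not follow from d/s = 0.45 at 80% power, and it conflicts with the 158 in section 1.4. Because 1.4 prints no SD, the conflict is over the same 6.3 points; 158 fits SD 14 exactly.

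Not shown, rather than shown to be false: that the additional 40 also covers conservative imputation. The arithmetic accounts for the 40 entirely as replacement of 20% losses. If about 20% of the FAS is imputed by JtR and 6.3 is the completer difference, I-QOL power at 99 per arm is roughly 64–71% without covariate gain, about 68–75% at a correlation of 0.3 and 77–83% at 0.5. It stays near 80% if no more than about 7.5–11% is imputed, and 80% is kept if 6.3 is already the FAS difference. The documents do not say which case applies.

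A reader might reach about 61% from a closed formula with an observed-patients standard error. That is a bound which simulated JtR with Rubin's rules does not reach, so it should not be quoted as the expected power.

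The primary endpoint, ICIQ-SF and type I error are not at risk.

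**What to change.** Keep N = 198 and the analysis as planned.

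- In section 8.4, replace 2 × 90 for I-QOL with d/s = 6.3/14 = 0.45, power 80%, N = 2 × 79 = 158, to match section 1.4. Relabelling 2 × 90 as 85% would leave two bases in the protocol and is not enough.
- In both sections, state that the 40 is a 20% drop-out allowance (158/0.8 = 197.5), if that is the sponsor's assumption.
- Then do one of two things. Either restate I-QOL and PAM-13 power for the planned FAS/JtR ANCOVA at that rate, saying whether 6.3 is the difference before or after imputation and naming the JtR variance method. Or withdraw the statement that the allowance also covers conservative imputation.

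The cost is a few words in two sections and a line in the SAP, which is still to come according to section 8.12: "A detailed statistical analysis plan (SAP) is created before the evaluation". No patients are added. The downside is that the stated power for the secondary endpoints may look somewhat less favourable.
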